### EQ-5D

By placing a tick in one box in each group below, please indicate which statements best describe your own health state today.

**Mobility**

- I have no problems in walking about
- I have some problems in walking about
- I am confined to bed

**Self-Care**

- I have no problems with self-care
- I have some problems washing or dressing myself
- I am unable to wash or dress myself

**Usual Activities** (e.g. work, study, housework, family or leisure activities)

- I have no problems with performing my usual activities
- I have some problems with performing my usual activities
- I am unable to perform my usual activities

**Pain / Discomfort**

- I have no pain or discomfort
- I have moderate pain or discomfort
- I have extreme pain or discomfort

**Anxiety / Depression**

- I am not anxious or depressed
- I am moderately anxious or depressed
- I am extremely anxious or depressed

## Your Quality of Life

Please think about your life right now. Whether your life is good or bad, we still want to know. Think about your blood glucose control and what you currently need or don't need to do (eg blood tests, insulin, waiting for a transplant, anti-rejection medication). Please tick one box  on each line.

My blood glucose and what I need to do to manage it mean ...	Strongly disagree	Disagree	Neither agree nor disagree	Agree	Strongly Agree	N/A
1. ...I can have the sort of relationship I would like with my family eg parents, brothers, sisters, children, grandchildren						
2. ...I can have the sort of relationship I would like with friends eg visiting, mutual support, shared interests / experiences						
3. ...I can go out or socialise as I would like eg cinema, concerts, eat or drink with friends, go to busy or crowded places						
4. ...I can have the sort of relationship I would like with a partner / spouse eg mutual support, sharing interests / experiences						
5. ...I can enjoy sexual activity as I would like eg spontaneity, frequency, ability						
6. ...I can be as physically active as I would like eg walking, gardening, shopping, sports						
7. ...I feel as well as I would like eg feel fit and healthy, no symptoms, healthy weight, enough energy						
8. ...I feel as in control of my body as I would like eg no highs and lows, can start a family						
9. ...I look as good as I would like eg look healthy, wear the clothes I want (no worries about hiding pump)						
10. ...I can have the holidays I would like eg accommodation, location, travelling						
11. ...I can work as I would like eg have responsibility, earn money, progress in my career, full- or part-time						
12. ...I have enough money						

My blood glucose and what I need to do to manage it mean ...	Strongly disagree	Disagree	Neither agree nor disagree	Agree	Strongly Agree	N/A
eg to pay bills, transport costs, food, gifts						
My blood glucose and what I need to do to manage it mean ...	Strongly disagree	Disagree	Neither agree nor disagree	Agree	Strongly Agree	N/A
13. ...I can drive as much as I would like eg to go shopping, give lifts to people, get to work, go out alone						
14. ...I can practise my religion / follow my beliefs as I would like eg go to my place of worship, be part of the community						
15. ...I can look after my home as I would like eg cooking, cleaning, decorating, repairs						
16. ...I can enjoy relaxing pastimes as I would like eg TV, hobbies, reading, computer games						
17. ...I can sleep as I would like eg get to sleep, stay asleep, feel rested						
18. ...I can eat as I would like eg when, where, what, as much or as little as I want						
19. ...I can look after or be as useful to others as I would like eg family, friends, colleagues, pets / animals, volunteering						
20. ...I can enjoy being with my pets / animals as much as I would like eg exercising, grooming, playing						
21. ...I can be as independent as I would like eg look after myself, go out alone, work or stay at home alone						
22. ...I can control my life as I would like eg freedom, choices, planning ahead, keeping appointments						
23. ...I can be as spontaneous as I would like						

	eg go out without notice, stay out as long as I want						
24.	...I can do "normal" things eg enjoy everyday life, do what other people do without worry						
25.	...I am treated as "normal" eg trusted to look after myself, capable, like any other person my age						
26.	...I have the confidence I would like eg alone or with others, able to take on challenges						

**Adult Low Blood Sugar Survey (University of Virginia) / Fear of Hypoglycaemia Survey**

I. **Behaviour:** Below is a list of things people with diabetes sometimes do in order to avoid low blood sugar and its consequences. Tick the box that best describes what you have done during the last 6 months in your daily routine to AVOID low blood sugar and its consequences. **(Please do not skip any!).**

To avoid low blood sugar and how it affects me, I ...	Never	Rarely	Sometimes	Often	Almost always
1. ate large snacks					
2. tried to keep my blood sugar 4mmol/L or above					
3. reduced my insulin when my blood sugar was low					
4. measured my blood sugar six or more times a day					
5. made sure I had someone with me when I go out					
6. limited my out of town travel					
7. limited my driving (car, truck or bicycle)					
8. avoided visiting friends					
9. stayed home more than I liked					
10. limited my exercise / physical activity					
11. made sure there were other people around					
12. avoided sex					
13. kept my blood sugar higher than usual in social situations					
14. kept my blood sugar higher than usual when doing important tasks					
15. had people check on me several times during the day or night					

**Worry:** Below is a list of concerns people with diabetes sometimes have about low blood sugar. Please read each item carefully (do not skip any). Tick the box that best describes how often in the last 6 months you WORRIED about each item because of low blood sugar.

Because my blood sugar could go low, I worried about...	Never	Rarely	Sometimes	Often	Almost always
16. not recognising / realising I was having low blood sugar					
17. not having food, fruit or juice available					
18. passing out in public					
19. embarrassing myself or my friends in a social situation					
20. having a hypoglycaemic episode while alone					
21. appearing stupid or drunk					
22. losing control					
23. no-one being around to help me during a hypoglycaemic episode					
24. having a hypoglycaemic episode while driving					
25. making a mistake or having an accident					
26. getting a bad evaluation or being criticised					
27. difficulty thinking clearly when responsible for others					
28. feeling lightheaded or dizzy					
29. accidentally injuring myself or others					
30. permanent injury or damage to my health or body					
31. low blood sugar interfering with important things					
32. becoming hypoglycaemic during sleep					
33. getting emotionally upset and difficult to deal with					

## **Appendix 6 – Phone script for recruitment**

**HIC #2000020059**

### **Phone script for recruitment for Counterregulatory failure and hypoglycemia unawareness in intensively treated older adult type 1 diabetic patients.**

This is XXX calling from the Yale Diabetes Center about a research study opportunity. I was looking at your pre-screen questionnaire through the Yale Center for Clinical Investigation database you had agreed to participate in. I would like to tell you about our current research to see if you might be interested in participating.

This research study is designed to demonstrate that a new closed loop insulin pump system can prevent low glucose episodes and enhance brain function in older patients with type 1 diabetes mellitus. We are looking for participants with Type1 Diabetes Mellitus, or T1DM, and who are over the age of 50, who have a history of frequent and/or severe episodes of low glucose values. Based on your pre-screen/screen information, you may be eligible.

Here is a little bit of a background information: As of right now, the best current treatment for T1DM is a sensor-augmented insulin pump therapy (so called “predictive low glucose suspend”; PLGS), which consists of an insulin pump that can “talk” with a continuous glucose monitor and can stop insulin injection in the presence of low glucose values. This feature limits duration and extent of hypoglycemic episodes that can frequently occur with traditional systems of insulin delivery.

In this study we will focus on the potential benefits of 2 FDA approved PLGS systems (Medtronic Minimed 670G and Tandem t:slim X2). These systems have been shown to effectively prevent hypoglycemia in the general patient population. Our hypothesis is that it would be safe and effective in reducing low glucose episodes specifically in older diabetic people.

To demonstrate this hypothesis, we will compare two groups of T1DM subjects for 8-10 weeks. As needed in this kind of scientific investigations, you will have the same probability to be assigned in one group or another and this decision will be independent from your or our determination. The intervention group consists of treatment with a PLGS-enabled insulin pump/CGM combination (Medtronic MiniMed 670G pump with Guardian sensor, or Tandem t:slim X2 pump with Dexcom sensor) in auto mode for Medtronic users and with Basal-IQ for Tandem users; subjects in the control group will use the same PLGS-enabled insulin pump/CGM combination but in manual mode for Medtronic users or without Basal-IQ for Tandem users. For subjects who use multiple daily injections as part of their standard insulin therapy or for subjects who do not use the MiniMed 670G pump or t:slim X2 pump, a loaner MiniMed 670G system will be provided.

To become a volunteer in this study, we’ll first have to schedule a 1-hour screening visit at the Yale New Haven Hospital Research unit. As part of this visit, we’ll go over the consent form with more details about

the study; you will have a blood draw, an EKG, a brief physical and a short cognitive test for our baseline information. If you qualify for the study, we'll be able to schedule your trial days at that point.

The trial itself consists of several sessions, of which two are 2 "questionnaire sessions", each 8 weeks apart, where you will be asked to complete a battery of tests to measure your cognitive abilities, quality of life and satisfaction of current insulin therapy. These take 2.5 hours each. Then there are 2 "hypoglycemic sessions" in an MRI machine, each 8-10 weeks apart and 2 days immediately after the 2 questionnaire sessions. There will be 7 brief weekly visits in between, either by phone or in person if needed, to check your glucose values and to ascertain that everything is going well.

The hypoglycemic sessions will take place in the early morning and you'll be asked to arrive fasting. The visit will last no longer than 4 hours and the time in the MRI scanner will be no longer than 130min. At the end of first of the 2 sessions you may be asked to continue your standard insulin pump therapy or to receive the new AC/AP pump for 8-10 weeks. You will be discharged home during the early afternoon.

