After completion of the first MRS session, subjects will randomized to either the intervention or control group. The intervention group consists of treatment with a PLGS-enabled insulin pump/CGM combination (Medtronic MiniMed 670G pump with Guardian sensor, or Tandem t:slim X2 pump with Dexcom sensor) in auto mode for Medtronic users and with Basal-IQ for Tandem users; subjects in the control group will use the same PLGS-enabled insulin pump/CGM combination but in manual mode for Medtronic users or without Basal-IQ for Tandem users. All subjects will undergo a PLGS system training session with a study nurse or nurse practitioner. Subjects will have weekly phone calls with study team members (physician and/or advanced practice nurse or registered nurse) to review blood glucose logs and insulin doses, potential adverse events, and other clinical or device-related issues. Subjects can also speak with a study physician, advanced practice nurse or registered nurse more frequently if there are any questions or concerns.

The two pump devices that will be used are: Medtronic MiniMed™ 670G system or Tandem t:slim X2 with Control IQ software. For subjects who use multiple daily injections as part of their standard insulin therapy or for subjects who do not use the MiniMed 670G pump or t:slim X2 pump, a loaner MiniMed 670G system will be provided. For subjects who use multiple daily injections as part of their standard insulin therapy, the training and support described above will be provided and may potentially be provided on a more frequent and/or intensive basis depending on the needs of the subject. A washout is not required given that regardless of method of administration (pump or injection), the insulin and dosages remain the same. Likewise, the risks remain similar. Furthermore, regardless

of the method of administration that the subject uses in their usual standard of care, all subjects will be trained and supported as much as is necessary in order to ensure that they understand how to use the PLGS system, and any subject who, in the opinion of the clinical study staff, is deemed to not be able to safely use the system will not continue in the study.

Program on Aging field core staff will remain in close contact with study participants via phone to identify and eliminate any obstacles to successful study completion.

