**Purpose (healthcare version):** The goal of this proposal is to implement a Predictive Low Glucose Suspend (PLGS) system in older patients with type 1 diabetes mellitus (T1DM) in order to reverse brain metabolic adaptations and restore metabolic sensitivity, hypoglycemia awareness and appropriate

hormonal counterregulatory responses (CRR). For purposes of this study we are looking to enroll aged T1DM subjects.

**Purpose (subject friendly version):** We are trying to demonstrate that a new insulin pump system can prevent low glucose episodes and improve brain function in aged T1DM subjects.

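### Recruitment texts state the hoped-for benefit as the study's purpose in a trial with no described masking, and the phone script gives two conflicting accounts of the control arm

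*Combined protocol and SAP*

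**What the plan says.** **Purpose.** The phone script in Appendix 6 says: "This research study is designed to demonstrate that a new closed loop insulin pump system can prevent low glucose episodes and enhance brain function". The subject-friendly web text in Section III, item 3 (Recruitment Procedures) says: "We are trying to demonstrate that a new insulin pump system can prevent low glucose episodes and improve brain function in aged T1DM subjects". The script adds: "These systems have been shown to effectively prevent hypoglycemia in the general patient population". It also has balancing text: "Our hypothesis is that it would be safe and effective in reducing low glucose episodes specifically in older diabetic people", and, on allocation, "you will have the same probability to be assigned in one group or another".

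**Control arm.** Section I, item 3 (Research Plan), in its overview and in part d on randomization, states: "subjects in the control group will use the same PLGS-enabled insulin pump/CGM combination but in manual mode for Medtronic users or without Basal-IQ" (the last phrase applies to Tandem users). People on injections, or on a pump other than the two named, are lent a 670G, and no restriction by arm is stated. Appendix 6 first repeats this description and the loaner provision. In its last paragraph it says of the end of the first clamp session: "you may be asked to continue your standard insulin pump therapy or to receive the new AC/AP pump for 8-10 weeks".

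**Outcomes.** The only hypothesis with a stated test and power is frontal cortex acetate utilization by MRS (Section I, Statistical Considerations). Research Plan part c adds questionnaires on awareness, quality of life and satisfaction with insulin therapy. Part b adds a symptom rating at the end of each clamp.

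**The concern.** Where participants know their allocation and rate themselves, what they were told to expect can influence the ratings. Both recruitment texts announce the favourable answer, including better brain function, as the thing to be shown. A person assigned to have the automation on can then report more benefit, and a person assigned to have it off can report less, without any true difference. Restored hypoglycaemia awareness is a stated goal of the study (Section I, Statement of Purpose), so one of the exposed outcomes matters to the trial's own argument.

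The control-arm sentence is a separate fault. It presents the comparison as usual pump against new pump, whereas the design compares one pump system under two settings. The listener hears two incompatible accounts of what the control group will do.

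**Working it through.** No arithmetic applies. The plan's one stated sample size, 12 per group raised to 15, concerns the MRS endpoint and does not bear on this point. The check sets the texts side by side.

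1. **Is masking described?** The design is a single-site, parallel-group randomized trial. No masking of participants or assessors is stated. In the plan's own text, blinding is mentioned only for the screening CGM (Section I, item 5). Participants are trained on the system and use it daily, in auto or manual mode, or with or without Basal-IQ. The documents never call the trial open-label; that is an inference, but a safe one.

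2. **Which outcomes can expectation reach?** Awareness, clamp symptoms, satisfaction and quality of life are self-reports. The MRS measure and the counterregulatory hormones are not. The documents give no labelled list of secondary outcomes. I call the questionnaires secondary because only the MRS hypothesis has a test and a power statement.

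3. **When could it act?** Randomization follows the first MRS session, and the first questionnaire session is scheduled before that session. Baseline ratings are therefore made before anyone knows the allocation. A difference between arms could arise in the ratings after the 8 to 10 weeks of pump use.

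4. **Does the balancing text cover the claim?** In part. The hypothesis sentence concerns safety and fewer low-glucose episodes. It says nothing about brain function, so that claim stands in the script without qualification. The protocol is more cautious: background part f says it has not been determined how far these systems can reverse the brain's metabolic adaptations, and Section V expects no direct medical benefit for subjects.

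5. **Do the control-arm descriptions agree?**

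| Source | What a control participant does |
|---|---|
| Research Plan, overview and part d | Uses the same pump/CGM combination, manual mode or without Basal-IQ |
| Appendix 6, earlier paragraph | The same |
| Appendix 6, last paragraph | Continues standard pump therapy; the other group gets a new pump |

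The third row conflicts with the first two. It cannot be right for injection users, who have no pump therapy to continue, or for users of other pumps, who receive a loaner. The abbreviation for the new pump is not spelled out. The closed-loop label in the purpose sentence also does not describe Basal-IQ, which the Research Plan presents as a predictive suspend feature.

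**The case against.** The strongest reply is that the script, read as a whole, is not one-sided. It describes the control arm correctly before the faulty sentence, mentions the loaner pump, calls the reduction in lows a hypothesis and states equal allocation. Subjects then go through the consent form, have the study explained in detail, complete a run-in and a first MRS session, and receive training. The script addresses people from one volunteer database; others come through clinics, flyers, referrals or MyChart. The consent form and the MyChart message were not available for this review, so what participants as a whole were told cannot be judged from these two texts. Participants using a visibly automated, FDA-approved system would also hold expectations however the text is worded.

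Most of this stands, and it limits the point. It rules out saying that the script simply misdescribes the control arm: the fault is an internal contradiction. It also means that the lack of masking, more than the wording, is the main source of exposure. It does not justify keeping a sentence that conflicts with the design, or a brain-function claim that nothing in the script balances.

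A reader might go further and infer that every self-report will be shifted by some fraction of a standard deviation, or that disappointed controls will drop out and use up the three extra participants per group. The documents support neither. They give no size for an expectation effect, nothing links the script to drop-out, and the three extra participants are a general allowance for missing values.

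**Conclusion.** The point holds as a minor one. Two recruitment texts present the expected benefit as what the study will show, in a trial with no described masking. This can add expectation bias to awareness, clamp symptoms, satisfaction and quality of life. One sentence in the phone script contradicts both the Research Plan and the script's own earlier paragraph.

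The bias cannot be sized from the documents, and no figure is offered. The conclusion assumes that participants know their pump setting and that the wording they meet at recruitment has some influence on later ratings. The first is a safe inference; the second is plausible but not shown. The primary MRS comparison and the hormone responses are not self-reported, and nothing here bears on the sample size.

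**What to change.** 1. In the yalestudies.org text and the opening of the phone script, replace the purpose sentence with a neutral one limited to older adults. For example: *We are comparing a study insulin pump with its automatic low-glucose feature on or off, and do not know whether this helps older adults with type 1 diabetes.* The limit to older adults is needed because the documents cite reductions in hypoglycaemia in other groups. The wording should not imply a single device, since two pump platforms are used.

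2. In the last paragraph of the phone script, replace the sentence offering standard therapy or a new pump with one consistent with the Research Plan and the script's earlier paragraph.

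3. Before reusing Research Plan text, reconcile two points in it. The Tandem software is named as Basal-IQ in one place and Control IQ in another (part d; also Section II, Devices). Manual mode is defined as having no sensor modulation, yet the text allows SmartGuard to be enabled at the clinicians' discretion. Participant wording about a feature being on or off has to match whatever is settled.

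4. Check the consent form and the MyChart message for the same phrasing.

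The cost is a text edit to two recruitment documents and an HIC submission. No procedure, sample size or analysis changes. The edit lowers expectation effects but does not remove them, so self-reported results should still be interpreted as unmasked.
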